1.2.7 Drug product

For a more detailed description of the Spesolimab profile, please refer to the current investigator's Brochure (IB) [[c03320877](#)].

1.3 RATIONALE FOR PERFORMING THE TRIAL

A recently completed Japanese Phase I trial (1368-0009) explored safety, tolerability, and PK of Spesolimab following IV administration of single-rising- doses (300, 600, 1200 mg) and single SC dose (300 mg) in healthy Japanese male subjects. In this trial, the Spesolimab exposure after IV administration increased with increasing dose in a dose-proportional manner across the tested dose range from 300 mg to 1200 mg. The relative bioavailability of Spesolimab after 300 mg SC administration was 73.5%. The dose-normalised exposure maximum measured concentration of the analyte in plasma (C_{max}) and Area under the concentration-time curve of the analyte in plasma over the time interval from 0 extrapolated to infinity ($AUC_{0-\infty}$) after single IV administration of Spesolimab were comparable and no large differences were observed between Japanese healthy subjects (trial 1368-0009) and non-Japanese healthy subjects (trial 1368-0001 and trial 1368-0002). The similar Spesolimab exposures was observed between Japanese healthy subjects and non-Japanese healthy subjects after single SC dose (300 mg; trial 1368-0009 and trial 1368-0003). The evaluation of the relative bioavailability between 300 mg SC and 600 mg SC was completed with Caucasian healthy volunteers (1368-0029).

The current trial will investigate the PK and safety of Spesolimab in healthy Chinese subjects. At the consultation meeting with NMPA held on Dec 2018, therapeutic dose was required to evaluate in this trial. The dose amount was set to cover the therapeutic dose of all indications.

1.4 BENEFIT - RISK ASSESSMENT

Participation in this trial is without any (therapeutic) benefit to healthy subjects. Their participation in the trial, however, is of major importance to the development of a new therapy

The subjects are exposed to the risks of the trial procedures and the risks related to the exposure to the trial medication.

Procedure-related risks

The use of an indwelling venous catheter for the purpose of blood sampling, may be accompanied by mild bruising and also, in rare cases, by transient inflammation of the wall of the vein. In addition, in rare cases a nerve might be injured while inserting the venous catheter, potentially resulting in paresthesia, reduced sensibility, and/or pain for an indefinite period. The same risks apply to vein puncture for blood sampling. Other risks of related to trial-specific procedures include IV infusion or SC administration of study medication, which can cause local bruising, inflammation, nerve damage and pain.

Proprietary confidential information © 2021 Boehringer Ingelheim International GmbH or one or more of its affiliated companies

The total volume of blood withdrawn during the entire trial per subject will not exceed the volume of a normal blood donation (400 mL). No health-related risk to healthy subjects is expected from this blood withdrawal.

Drug-related risks and safety measures

The toxicology package conducted in mice with a mouse-specific antibody (BI 674304) includes 4-, 13- and 26-week toxicity studies and reproductive/developmental toxicity studies without any findings which would preclude clinical studies in humans (see IB [[c03320877](#)]). There have been no dose or exposure-related abnormalities in safety laboratory parameters and no safety or tolerability concerns that would preclude further clinical development of Spesolimab.

Spesolimab has been tested and found safe and tolerable in humans in single- and multiple-rising-dose trials 1368-0001, 1368-0002, 1368-0003, 1368-0009 and 1368.29 in healthy male and female subjects and in trial and in several completed trials in patients

No clinically relevant abnormalities on treatment with Spesolimab with respect to safety laboratory parameters and vital signs were observed (see IB [[c03320877](#)]).

Based on studies in healthy subjects and patients, no specific drug-related risks are anticipated. Nevertheless, the following safety measures are/will be applied in this trial in order to minimise the risk for the healthy subjects:

- Careful dose selection based on data of the completed studies. In the first dose group of 300 mg SC, the exposure is projected to be similar to the Japanese healthy subjects who were enrolled in trial 1368-0009 and received the same SC dose.
- For the IV dose groups, the administration as 90 minutes infusion allows immediate discontinuation of drug administration should any safety concern arise.
- For both IV and SC dose groups, a time interval of at least two weeks will be maintained between first administration of trial medication in the actual dose level and first administration in the next dose level, which is expected to cover the period of highest risk/peak effect. The next dose will only be given if no safety concerns arise in the previous dose group and if none of the pre-specified trial-specific stopping criteria are met within each IV and SC dose groups.
- Extensive monitoring of 12-lead ECG and vital signs is incorporated, with 12-lead ECG to cover the anticipated period of highest drug exposure. As an additional measure, repeated single 12-lead ECGs are scheduled in the further course of the trial. The rationale for the intensified 12-lead ECG monitoring is not due to expected increased risk of Spesolimab mediated effects on cardiac repolarization, rather, it is been implemented to collect 12-lead ECG data at an early point in clinical development to perform 12-lead ECG interval assessment under drug. In general, for biologics, Time between start of the Q-wave and the end of the T-wave in an electrocardiogram (QT) prolongation is not usually an issue unless there are mechanistic effects with the mAb which can lead indirectly to the 12-lead ECG changes [[R09-2768](#)] but this is not expected to be the case for Spesolimab.
- Extensive safety laboratory testing will be performed.

Proprietary confidential information © 2021 Boehringer Ingelheim International GmbH or one or more of its affiliated companies

- After each dosing, the subjects will stay at the site for at least 48 hours following drug administration.
- During in-house-confinement the subjects will be under close medical observation and thoroughly monitored for both expected and unexpected AEs.
- Close monitoring of subjects' signs and symptoms for hypersensitivity reactions during and after trial drug administration. Hypersensitivity reactions should be treated according to local medical standards [\[R11-4890\]](#).

Currently there are no data available to suggest interactions of Spesolimab [\[c03320877\]](#).

Although rare, potential for drug-induced liver injury (DILI) will be under constant surveillance by sponsors and regulators. Therefore, this trial requires timely detection, evaluation, and follow-up of laboratory alterations in selected liver laboratory parameters to ensure subjects' safety; see also [section 5.2.6.1.4](#), AEs of special interest.

As an antagonist of IL36R, Spesolimab affects one target of the immune system which is ubiquitously expressed. Due to the antagonistic effect, it is considered remote that Spesolimab may lead to an amplification of an effect that might not be sufficiently controlled by a physiologic feedback mechanism. In addition, preclinical investigations and BI's clinical programme have demonstrated no cases of cytokine release syndrome induced by Spesolimab to date.

Due to the lack of mechanism- or compound-related safety signals and the antagonistic mode of action of Spesolimab, it is considered that healthy subjects will not be exposed to undue risks in relation to the information expected from this trial. Considering the medical need for the development of an effective and well-tolerated drug for the therapy of

the expected benefit of this trial is considered to outweigh the potential risks and justifies the exposure of healthy subjects.

Benefit-Risk Assessment in context of COVID-19 pandemic for subjects participating in clinical trials investigating Spesolimab:

A thorough assessment has been conducted to evaluate whether spesolimab may pose a higher risk associated with COVID-19 infection. The key aspects of the assessment are summarized below.

Spesolimab is an immune-modulating humanized monoclonal antibody that blocks the human IL-36 receptor and thereby the pro-inflammatory IL-36 pathway. Available non-clinical and clinical data in 604 subjects (see [c03320877](#)) have not shown an increased risk of infections with spesolimab. However, similar to other immune modulating biological treatments, spesolimab may hypothetically increase the risk of infections. Therefore, risk mitigation measures, such as close monitoring of adverse events, as well as guidance on handling of acute infections occurring during the trial have been included within this clinical trial protocol.

The investigator may choose to perform COVID-19 testing as per his/her discretion if useful based on individual medical consideration and in the case of suspected COVID-19 infection.

Proprietary confidential information © 2021 Boehringer Ingelheim International GmbH or one or more of its affiliated companies

As any other acute infection, a suspected or diagnosed COVID-19 infection should be treated according to the standard of care.

The investigators will take the totality of information related to each single subject and the local COVID-19 situation into consideration when performing the individual benefit-risk assessment on a case-by-case basis. Considering all aspects, the investigator will decide upon each subject's (continued) participation in the planned trials. BI as the sponsor, where required, will support the investigator in their decision finding. It is acknowledged that the investigator may decide to implement protocol deviations where this protects the safety, wellbeing, and/or is in the best interest of the patient.

To address potential risks associated with operational aspects related to the participation in clinical trials in context of COVID-19 pandemic, different risk mitigation measures are considered in ongoing and planned spesolimab clinical trials based on local requirements and development of the pandemic.

The benefit-risk assessment of spesolimab remains favourable in the context of the COVID-19 pandemic.

2. TRIAL OBJECTIVES AND ENDPOINTS

2.1 MAIN OBJECTIVES, PRIMARY AND SECONDARY ENDPOINTS

2.1.1 Main objectives

The primary objective of this trial is to investigate PK, including dose proportionality, following single IV and SC doses of spesolimab in healthy Chinese subjects.

[figure not shown]

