Diagnosis	Not applicable
Main criteria for inclusion	Healthy male or female subjects (at least three subjects for each gender within each dose group) Age of 18 to 45 years (inclusive) Body weight \geq 50 kg for male and \geq 45 kg for female Body mass index (BMI) \geq 19 and $<$ 26 kg/m ² for male and female at visit 1
Test product 1	BI 655130 (60 mg/mL) solution for infusion
dose	Single dose of 450 mg, 900 mg and 1200 mg
mode of admin	IV as 90 min infusion
Test product 2	BI 655130 (150 mg/mL) solution for injection
dose	Single dose of 300 mg and 600 mg
mode of admin	SC injection
Comparator product	Not applicable
dose	Not applicable
mode of admin	Not applicable
Duration of treatment	One day (single dose) for each treatment
Statistical methods	Descriptive statistics will be calculated for all endpoints. Dose proportionality of Spesolimab will be explored using a regression model for AUC _{0-∞} and C _{max} for IV doses. A 90% confidence interval (CI) for the slope will be computed.

FLOW CHART S.C.

Single dose group for SC

Single dose of Spesolimab as 300 mg and 600 mg SC (subjects will receive only one dose)

Visit	Day	Time relative to first drug administration (planned time) [h:min]	Approx. time (actual time) [h:min]	Event and comment	PK _{blood} ⁴	Plasma ADA ⁸	Laboratory ³	Body weight	12-lead ECG	Vital signs (BP, PR, RR, body temperature) ¹⁰	Query on AEs, concomitant therapies ¹¹
1	-28 to -3			screening ¹			X ¹⁴	X	X	X	
	-2	-48:00	8:00	ambulatory visit			X ¹³				X ¹³
2	-1	-12:00	20:00	admission to trial site			X ⁹				X
1	1	-2:00	6:30		X ²	X ²	X ^{2,14}		X ²	X ²	X ^{2,5}
		0:00	8:00	drug administration							
		0:10	8:10							X	
		0:30	8:30		X				X	X	X ⁵
		1:00	9:00							X	
		1:30	9:30						X	X	
		2:00	10:00	light breakfast ⁶	X				X	X	
		3:00	11:00		X					X	
		4:00	12:00	lunch ⁶	X					X	X ⁵
		6:00	14:00						X	X	
		8:00	16:00		X					X	
		10:00	18:00	dinner ⁶							
		12:00	20:00		X				X	X	X ⁵
2	2	24:00	8:00	breakfast ⁶	X				X	X	X ⁵
		28:00	12:00	lunch ⁶							
		32:00	16:00							X	
		34:00	18:00	dinner ⁶							X ⁵
3	48:00	8:00		breakfast ⁶ discharge from trial site (confirmation of fitness) ⁷	X				X	X	X ⁵
4	72:00	8:00		ambulatory visit	X		X				X ⁵
5	96:00	8:00		ambulatory visit	X						X ⁵
6	120:00	8:00		ambulatory visit	X						X ⁵
7	144:00	8:00		ambulatory visit	X						X ⁵
8	168:00	8:00		ambulatory visit	X		X		X	X	X ⁵
15	336:00	8:00		ambulatory visit	X	X					X ⁵
22	504:00	8:00		ambulatory visit	X		X		X	X	X

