4.1.2 Selection of doses in the trial

Dose strengths will be investigated for both SC administration and IV administration in this trial. Doses for SC and IV will each cover potential therapeutic dose ranges and provide a safety margin for future development. Dose proportionality of exposure will be evaluated for IV group.

This trial is designed to evaluate the PK and safety of Spesolimab in Chinese healthy subjects.

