7. STATISTICAL METHODS AND DETERMINATION OF SAMPLE SIZE

7.1 STATISTICAL DESIGN – MODEL

The primary objective of this trial is the evaluation and comparison of several PK parameters between all tested treatments, including an evaluation of dose proportionality for those in the IV dose groups. Endpoints as specified in [section 2.1.2](#) will be assessed using descriptive statistics. $AUC_{0-\infty}$ and C_{max} for IV doses will be subjected to analysis of dose proportionality by use of the power model.

The secondary objective of this trial is the evaluation of safety and will be evaluated by descriptive statistics.

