5. ENDPOINTS

5.1 PRIMARY ENDPOINTS

The primary objective of this trial is to investigate PK, including dose proportionality, following single IV and SC doses of Spesolimab in healthy Chinese subjects. Primary endpoints are $AUC_{0-\infty}$ and C_{max} of Spesolimab.

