7.4 PRIMARY ENDPOINTS

7.4.1 Primary analysis of the primary endpoints

Section 7.1.3 of the CTP: *The primary endpoint as specified in [Section 5.1](#) will be derived according to BI standards (BI-KMED-TMCP-MAN-0014). The analysis will be based on the PKS and will be descriptive in nature.*

For IV doses the dose proportionality of $AUC_{0-\infty}$ and C_{max} will be analysed.

Assessment of dose proportionality

Dose proportionality will be explored via graphical checks and if applicable via the power model stated below. The analysis will be performed for the PK endpoints AUC/C_{max} specified in section 5.1.

The power model describes the functional relationship between the dose level and PK endpoint on the log scale via

$$y_{km} = \log(x_{km}) = \mu + b \cdot \log(D_k) + e_{km},$$

where

- y_{km} logarithm of response (PK parameter) measured on subject m^{th} receiving dose k ,
- μ the overall mean,
- β slope parameter of linear regression line,
- D_k level of dose k , $k=1, 2, 3$,
- e_{km} the random error associated with the m^{th} subject who was administered dose k ($e_{km} \sim N(0, \sigma^2)$ iid).

This equation can be fit as a linear regression model.

The slope parameter β together with its two-sided 90% confidence interval will be estimated. Perfect dose proportionality would correspond to a slope of 1. Additionally, the r -fold change $r^{\beta-1}$ together with its 90% CI will be derived.

Graphical displays:

A regression plot will be performed, where the logarithm of dose is depicted versus logarithm of PK endpoint, including the estimated regression line from the power model and reference line of perfect proportionality ($\beta=1$).

This analysis will be based on the PKS.

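### The primary objective names dose proportionality after SC doses, but the visible plan analyses it for IV only, with no SC ratio or confidence interval for AUC0-∞ or Cmax

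*Protocol*

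**What the plan says.** **Objective, both routes.** Protocol 2.1.1 states the primary objective as "to investigate PK, including dose proportionality, following single IV and SC doses of spesolimab in healthy Chinese subjects". SAP 5.1 repeats it: "to investigate PK, including dose proportionality, following single IV and SC doses of Spesolimab in healthy Chinese subjects". The synopsis also names both routes.

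**Analysis, IV only.**
- Synopsis, statistical methods: "Dose proportionality of Spesolimab will be explored using a regression model for" the two primary endpoints, for IV doses.
- Protocol 4.1.2: "Dose proportionality of exposure will be evaluated for IV group".
- Protocol 7.1 words the primary objective differently, as "evaluation and comparison of several PK parameters between all tested treatments", "including an evaluation of dose proportionality for those in the IV dose groups".
- Protocol 7.3.1 and SAP 7.4.1 ("For IV doses the dose proportionality of" AUC0-∞ and Cmax) specify graphical checks and, if applicable, a power model. The slope and the r-fold change each get a 90% CI. The dose index runs k = 1, 2, 3, which matches the three IV doses and not the two SC doses.

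**What SC gets.** SAP section 7 plans by-group summaries of the PK parameters, including N, geometric mean, geometric CV and percentiles. SAP 7.4.2, which would hold exploratory analyses of the primary endpoints, is marked not applicable. SAP section 4, which lists departures from the protocol, does not mention the difference between objective and analysis.

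**The concern.** An objective and its analysis should cover the same question. Here three statements of the objective promise dose proportionality for both routes, and five analysis statements deliver it for one. None of the five gives a reason.

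A reader of the trial report will look for an SC result because the objective names one, and will have to build it from descriptive tables. The method and confidence level would then be chosen after the data are known. The IV slope cannot stand in for it, because SC exposure also depends on absorption.

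The stakes are limited. Protocol 7.2 plans no hypothesis tests and treats all intervals as exploratory, so neither the IV result nor any error rate is affected.

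**Working it through.** **Plan's own figure.** Protocol 7.7 plans 5 groups × 10 = 50 evaluable subjects, and 50 + 10 replacements = 60 entered. This reproduces and is not in dispute. There is no power, margin or effect size to check.

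**Can the planned SC data support an estimate?** The calculation below compares its precision with that of the planned IV slope.

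*Inputs from the documents:* IV 450, 900 and 1200 mg; SC 300 and 600 mg; 10 evaluable per group; two-sided 90% CI.

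*Assumption:* between-subject CV of 20, 30 or 40%, the same for both routes. The documents give no CV.

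*Formulas:*
- SD on the log scale = √ln(1 + CV²) = 0.198, 0.294, 0.385.
- Sxx = n × Σ(ln dose − mean ln dose)².
- Half-width of the slope CI = t(0.95, df) × SD / √Sxx.
- Factor for the r-fold change = exp(half-width × ln r).

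*Design quantities:*
- SC: Sxx = 10 × 2 × (ln 2 / 2)² = 2.402; df = 18; t = 1.734.
- IV: Sxx = 10 × (0.558² + 0.135² + 0.423²) = 5.084; df = 28; t = 1.701.

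*Worked case, CV 30%:*
- SC half-width = 1.734 × 0.294 / √2.402 = 0.328.
- IV half-width = 1.701 × 0.294 / √5.084 = 0.221.
- SC ratio factor at r = 2: exp(0.328 × 0.693) = 1.256. An observed ratio of 1.00 would have a 90% CI of 0.80 to 1.26.

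| Quantity | CV 20% | CV 30% | CV 40% |
|---|---|---|---|
| SC slope half-width | 0.222 | 0.328 | 0.431 |
| IV slope half-width | 0.149 | 0.221 | 0.291 |
| SC 600:300 mg ratio, ×/÷ | 1.166 | 1.256 | 1.348 |
| Same, 8 evaluable per SC group (df 14, t = 1.761) | 1.191 | 1.295 | 1.404 |
| IV at r = 2, ×/÷ | 1.109 | 1.166 | 1.223 |
| IV over its full range, r = 1200/450 = 2.67, ×/÷ | 1.158 | 1.243 | 1.330 |

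The SC slope interval is 1.48 times as wide as the IV one at equal CV. Precision is similar only when each route is judged over its own dose range.

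**Equivalence.** With two doses, 2^(β−1) from the power model is exactly the dose-normalised 600:300 mg geometric mean ratio. The two-sample form exp(t × SD × √(2/10)) gives the same factors, so no new method is needed.

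**The case against.** The strongest reply is that IV only was intended. Protocol section 7, on which the SAP says it is based, is consistent on this, and Protocol 7.1 even words the primary objective that way. An analyst following the plan would not be in doubt. This stands as a reading of intent, but it leaves the objective wrongly worded in three places.

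Second, SAP section 7 places inferential PK analyses in 7.4.1 and 7.6. Neither SAP 7.6 nor Protocol 7.3.3 can be read in the public copy, so an SC analysis there cannot be excluded, and nothing is claimed here about other PK endpoints. However, AUC0-∞ and Cmax are primary endpoints, which the SAP handles in 7.4, and the conflict in the visible wording remains either way.

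Third, the SC geometric means and CVs are planned, so the ratio and an approximate interval can be worked out later. That is true, and it keeps the practical loss modest. What is missing is the pre-specification. The IV power model is itself exploratory and conditional, so the contrast is not between a firm analysis and none.

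Fourth, two dose levels cannot test log-linearity, and Protocol 1.3 reports that "The evaluation of the relative bioavailability between 300 mg SC and 600 mg SC was completed with Caucasian healthy volunteers". Both points lower the stakes. Neither supplies the estimate in Chinese subjects, and IV proportionality is re-estimated here although Protocol 1.2.5 and 1.3 already report it from earlier trials.

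**Conclusion.** The concern holds. The stated primary objective covers SC dose proportionality, and the visible plan pre-specifies no SC slope, dose-normalised ratio or CI for AUC0-∞ or Cmax. It should be corrected, but it does not threaten the trial: no planned figure is wrong, and the IV analysis is untouched.

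The precision figures describe the estimate that could be added; they are not a measure of error in the plan. They rest on the assumed CVs, on equal CV for both routes where the routes are compared, and on 10 (or 8) evaluable subjects per SC group. Within those assumptions, the SC interval would be wider than the IV one but still informative for exploratory use.

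**What to change.** **Preferred.** In SAP 7.4.1, add the dose-normalised 600:300 mg SC geometric mean ratio of AUC0-∞ and Cmax with a two-sided 90% CI, obtained as 2^(β−1) from the same power model fitted to the SC groups alone. Label it as exploratory and as a two-point comparison that cannot check log-linearity. Record it in SAP section 4 as an addition to the protocol analysis. The cost is a few lines of text and one extra table on data already collected. The drawback is an estimate of limited interpretability, wider than the IV one.

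**Alternative, if IV only is intended.** Align the objective in the synopsis, Protocol 2.1.1 and SAP 5.1 with Protocol 7.1. The synopsis and 2.1.1 would need a protocol amendment with the review described in Protocol 8.1; SAP 5.1 needs only a SAP revision.

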2.1.2 Primary endpoint

$AUC_{0-\infty}$ and C_{max} of spesolimab.

